- Haematology with differential* will be performed at Screening, Baseline, pre-dose on Day 1, and approximately every 3 days.
- Coagulation* will be performed at Screening, Baseline, pre-dose on Day 1, and then at least once weekly throughout the study.
- Biochemistry* will be performed at Screening, Baseline, pre-dose on Day 1, and then as follows:
 - Cohort 1: Days 3 and 7 of dosing, and Days 9, 11 and 14 of the rest period.
 - All other Cohorts, pending DSMC review of Cohort 1 data:
 - If clinically significant trends are noted by the DSMC, or an opinion has not yet been formed, then either focused panels or full biochemistry will be performed at least twice weekly throughout the Cycle.
 - If clinically significant trends are not noted by the DSMC, then full biochemistry panels will be performed at least once weekly throughout the Cycle.
- Urinalysis with microscopy will be performed at Screening, pre-dose on Day 1, and then at least once weekly throughout the study.
- Red Cell Haemoglobin F (HbF)** will be measured pre-dose on Day 1, at the end of dosing (sample timing will vary depending on the duration of the Cohort), and then on the last day of the rest period.
- Prostate Specific Antigen (PSA)** will be measured in males pre-dose on Day 1 and then on the last day of the rest period.

*To be performed at EOT, pre-EOS, and EOS visits.

**To be performed at EOT.

Cycle 2 and beyond, all Cohorts

- Haematology with differential (diff) will be performed pre-dose on Day 1 and approximately every 3 days throughout the duration of the study, at the EOT, pre-EOS, and EOS visits, and upon suspicion of relapse.
- Coagulation will be performed pre-dose on Day 1 and then at least once weekly throughout the study, at the EOT, pre-EOS, and EOS visits and upon suspicion of relapse.
- Biochemistry: Pending DSMC review of Cycle 1 data, biochemistry will be performed:
 - If clinically significant trends are noted by the DSMC, or an opinion has not yet been formed, then either focused panels or full biochemistry will be performed twice weekly throughout the Cycle.
 - If clinically significant trends are not noted by the DSMC, then full biochemistry panels will be performed at least once weekly throughout the Cycle.
 - At the EOT, pre-EOS, and EOS visits and upon suspicion of relapse.
- Urinalysis with microscopy will be performed pre-dose on Day 1 and then at least once weekly throughout the study, at the EOT, pre-EOS, and EOS visits and upon suspicion of relapse.

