6.4 Replacement of dropouts

A minimum of 3 patients per cohort/sub-cohort are required to complete the entirety of Cycle 1 (including the applicable treatment and rest periods). Contingent on the number of prior DLTs within a cohort/sub-cohort, non-completers of Cycle 1 will be replaced to ensure a minimum of 3 patients complete Cycle 1 of each cohort/sub-cohort.

CC

CCI

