c In Cycles 2 and 4 ONLY, BM and associated analyses will be performed															
d In Cycle 2 for all patients; also to be collected in Cycle 3 IF Day 7 through 14 PK was deferred to Cycle 2															
e 24 hours post Day 6 IMG-7289 dose and prior to next IMG-7289 dose (±1 hour)															
f PB sample may be used for either immunophenotyping or genomics, if the BM sample is inadequate for analysis purposes															
g Patients should take their IMG-7289 in the morning at approximately the same time every day															
h If the patient is completing the study, this visit will be replaced by the EOT visit															
i Exact time of dose on Day 6 (IMG-7289 and ATRA, if applicable) to be collected from patient and recorded in the source notes; patient should also be reminded to fast prior to Day 7 visit and that Day 7 morning dosing (IMG-7289 and ATRA, if applicable) will occur in the clinic															
k If Cycle 1 Day 7 through 14 PK was deferred to Cycle 2															
m In Cycle 4 ONLY															
n If applicable patients should take their ATRA in the morning and the evening at approximately the same time every day															
o In Cycle 3 ONLY, patients receiving 21 days continuous dosing with ATRA will continue to dose and return ATRA during the IMG-7289 rest period															
p In Cycles 2 and 4 ONLY, patients receiving 21 days continuous dosing with ATRA will return medication from the previous cycle.															

16.1.4 SoA: Cohorts 3 and 3x, Cycle 1

Visit Name	Treatment Period (D = Day)														Rest Period							
	Pre- Dose D1	Day														Day						
Visit Date		1	2	3	4	5	6	7	8	9	10	11	12	13	14	15	16	17	18	19	20	21
Medical History	X																					
Verify Patient Eligibility	X																					
Complete PE (incl vital signs)	X							X							X							X
Limited PE (incl vital signs)				X		X				X		X					X		X			
Concomitant Medications	←																					→
Adverse Event Collection		←																				→
Phone patient-Time of dose/fasting														X ^c								
LOCAL LAB SAMPLING:																						
Haematology with Diff	X			X		X		X		X		X			X		X		X			X
Coagulation (PT/PTT/INR)	X							X							X							X
Biochem – CS trends noted				X						X							X					
Biochem – standard	X							X							X							X
Urinalysis with Microscopy	X							X							X							X
Urine Pregnancy Test (WOCBP)	X							X							X							X
HbF	X														X							X
PSA (males)	X																					X

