The statistical analyses will be reported using summary tables, figures, and data listings. Unless otherwise noted, all statistical testing will be two-sided with significance being $p < 0.05$. Continuous variables will be summarized with means, standard deviations, medians, minimums, and maximums. Categorical variables will be summarized by counts and by percentage of patients in corresponding categories. As appropriate and where specified, continuous and categorical variables will be evaluated using the Student t-test, ANOVA, Wilcoxon rank sum, Fisher's exact, or χ^2 tests. As appropriate and where specified, summary tables will be presented by cohort, and may also include a "Total" or "All Patients" summary.

The analyses described in this plan are considered *a priori*, in that they have been defined prior to database lock. If any post-hoc analyses are performed they will be defined and reported in the CSR.

All analyses will be performed using SAS statistical analysis software (SAS, SAS/GRAPH and SAS/STAT; version 9.3 or higher of SAS for Windows [SAS Institute Inc; Cary, NC, USA]).

A. Data Sources

All data are collected *via* electronic case report forms (eCRFs) through remote data entry. Section 13.7 of the protocol describes data quality assurance.

B. Definition of Baseline

For analysis purposes, baseline is defined as the last assessment prior to the first dose of study drug. Cycle 1 Day 1 is the first day a patient receives study drug. For most measurements, baseline assessments will be taken pre-dose on Cycle 1 Day 1. If pre-dose assessments on Day 1 are not available, the most recent prior assessment closest to Day 1 may be substituted in some cases, and unless otherwise specified. For local laboratory data, baseline data will be obtained during the screening period (Days -28 to 1). All other baseline data will be collected on Days -21 to 1.

C. Missing Data

For safety and tolerability, missing data, including those not obtained because of death, will be the last value carried forward.

If CTCAE Grade is missing, the event is assumed to be 'Severe' (grade 3). If AE relatedness is missing, the event is assumed to be 'possibly' related.

Otherwise, missing data will not be replaced with imputed values. When relevant, sections below will address how missing data will be handled for the particular analyses.

D. Display and Imputation Methods for Missing Dates

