guidelines change, or are not followed adequately, treatment-emergent events will be identified programmatically per the above definition, using imputed start date.

Severity of AEs will be reported using the NCI CTCAE grades (v4.03) where Grade 1 is Mild, Grade 2 is Moderate, Grade 3 is Severe, Grade 4 is Life-Threatening, and Grade 5 is Fatal.

CCI

CCI

B. Other Safety Parameters

Changes in vital signs, laboratory values and ECGs will also be evaluated and assessed. Information on the timing of these assessments is presented in Protocol Section 9.

The following laboratory tests will be conducted:

- Complete blood counts (CBC) and differential
- Coagulation
- Chemistry panel including LFTs (AST, ALT, INR, total bilirubin, gamma glutamyltransferase (GGT), and albumin)
- Urinalysis with microscopy
- ECGs

Laboratory values will be listed and summarized at each assessment. Numerical laboratory results will be summarized with the actual values, change from baseline (CFB), percent CFB by visit. P-value for test to assess maximum and minimum change from baseline within each cohort will be calculated using paired t-test.

Shift tables for laboratory values with respect to normal range (low, normal, high) and CTCAE toxicity grade, compared to baseline, will be summarized by visit. Overall laboratory result shift from baseline (Normal, Abnormal clinically significant (CS), and Abnormal non-clinically significant (NSC)) will be summarized.

ECG parameters and vital sign assessments will be summarized with the actual values, change from baseline, and percent change from baseline by visit. P-value for test to assess maximum and minimum change from baseline within each cohort will be calculated using paired t-test. Additionally, overall ECG result shift from baseline (Normal, Abnormal clinically significant (CS), and Abnormal non-clinically significant (NSC)) will be summarized.

Physical exam data will be listed.

X. Additional Analysis

The additional analyses outlined here will be performed using the Safety Population.

A. Pharmacodynamics

Pharmacodynamics (PD) obtained from serial blood, bone marrow, and urine sampling at specified time points will be listed and summarized.

CCI

CCI

CCI

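### The within-cohort paired t-tests on maximum and minimum change from baseline do not hold 5%: at n=3 with nine post-baseline values they reject in about 11-25% of cases with no drug effect

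*SAP*

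**What the plan says.** SAP IX.B lists the laboratory tests, which include "Complete blood counts (CBC) and differential", and asks for actual values, change and percent change by visit. It then adds: "P-value for test to assess maximum and minimum change from baseline within each cohort will be calculated using paired t-test". The next part of IX.B says "ECG parameters and vital sign assessments will be summarized with the actual values, change from baseline, and percent change from baseline by visit" and repeats the t-test sentence. SAP X.A repeats it for the pharmacodynamic parameters, whose list is blacked out, so nothing is asserted here about any particular marker.

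The level comes from SAP VI: "Unless otherwise noted, all statistical testing will be two-sided with significance being" p<0.05. SAP VI.I plans no multiplicity control. For the reference value, "baseline is defined as the last assessment prior to the first dose of study drug" (SAP VI.B). The visible text does not define maximum or minimum change, does not limit the visits or cycles that enter it, and names no null value other than the zero implied by a paired t-test.

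On cohort size, Protocol 6.4 says "A minimum of 3 patients per cohort/sub-cohort are required to complete the entirety of Cycle 1".

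**The concern.** A paired t-test is valid for a change whose mean is zero when nothing happens. A change at one fixed visit has that property; the most extreme of several changes does not. With several noisy post-baseline values, each patient's maximum tends to be positive and the minimum negative. The null hypothesis is then false by construction, so adding patients makes false rejection more likely.

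The natural reading is one extreme per patient. The next paragraph of X.A sends maximum and minimum change to a Kruskal-Wallis test between cohorts, which needs one value per patient.

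Protocol 8.2.1 expects real falls in platelets and neutrophils. The problem therefore matters most where no effect is expected, such as vital signs, chemistry and coagulation. There the p-value could present a rise or fall produced by picking the extreme visit as a drug effect, and one measure could show a significant rise and a significant fall at once.

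**Working it through.** **Number of values per patient**

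- Cohorts 3/3χ, Cycle 1 (Protocol 16.1.4): haematology on Days 3, 5, 7, 9, 11, 14, 16, 18 and 21, so K=9 post-baseline values. Complete and limited examinations together put vital signs on the same nine days. Coagulation and standard chemistry are on Days 7, 14 and 21 only, so K=3.
- Cohort 1, Cycle 1 chemistry (Protocol Synopsis): "Days 3 and 7 of dosing, and Days 9, 11 and 14 of the rest period", so K=5.
- Cohort 1, Cycles 2-4 haematology (Protocol 16.1.3): pre-dose Day 1 and Days 4, 7, 9, 11 and 14. That is 6 per cycle, and 3 × 6 = 18 for a patient who completes all allowed cycles.
- Patients: n=3 is the planned minimum. n=5 is illustrative only.

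**Model.** Each patient has one baseline Y0 and later values Y1 to YK, with the same mean throughout (no drug effect). The changes are Dk = Yk − Y0. The test statistic is t = mean(M) / (SD(M)/√n), where M is each patient's maximum (or minimum) Dk, compared with the two-sided 5% point of t on n−1 degrees of freedom.

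**Check against the nominal level.** With K=1 the simulation gives 4.8-5.3%. A fixed last visit among many gives the same, so the code reproduces 5% where it should.

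**Size of the bias.** With nine independent values, the mean of each patient's maximum change is about 1.48 SD of a single value when the true change is zero.

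**Rejection of the test on maximum change, no drug effect** (40,000 replicates, normal data, all visits done). The three figures are random walk / serial correlation 0.8 / independent values, in %.

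| K | Where it arises | n=3 | n=5 |
|---|---|---|---|
| 3 | Cohorts 3/3χ Cycle 1 coagulation, standard chemistry | 7.5 / 8.1 / 11.0 | 12.6 / 14.2 / 21.0 |
| 5 | Cohort 1 Cycle 1 chemistry | 9.2 / 11.5 / 16.5 | 19.7 / 24.2 / 37.9 |
| 9 | Cohorts 3/3χ Cycle 1 haematology, vital signs | 11.3 / 16.1 / 24.9 | 28.1 / 39.8 / 57.9 |
| 18 | Cohort 1 Cycles 2-4 haematology | 13.6 / 23.5 / 34.6 | 37.9 / 60.2 / 76.8 |

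Equal correlation among the values gives the independent-values figure whatever its size (24.7-24.9% for K=9), because the part shared within a patient cancels in the change. A separate simulation of 200,000 trials gave the same 11-25% range for K=9 at n=3. It put the chance that at least one of the maximum and minimum tests rejects at 21-43%.

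**Skewed data.** By symmetry the minimum behaves like the maximum for normal data, but not for skewed data. With log-normal values (log SD 0.3-0.5, correlation 0.8 to 0) at n=3, the maximum and minimum tests reject 14-26% and 11-19% for K=9, and 21-38% and 15-26% for K=18.

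**Other reading.** If the visit with the extreme cohort mean is meant, the error at n=3 is 7-9% for K=9 and 9-11% for K=18 (correlation 0.8 to 0).

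**The case against.** Several points can be made for leaving the plan alone.

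- **The nine-value figure does not describe every measure.** This stands. Coagulation and standard chemistry in Cohorts 3/3χ have three values per cycle (about 8-11% at n=3), and two values give about 6-8%. A measure taken once after baseline is unaffected; ECG may be such a case. However, vital signs do have nine values, and the SAP does not confine the extreme to Cycle 1.
- **Cohorts 3 and 3χ may never open.** This also stands, because they depend on the DSMC. Cohort 1 gives 9-17% for Cycle 1 chemistry and 14-35% for haematology over Cycles 2-4, both at n=3.
- **The range is not a bound.** Correct. With nine values at n=3, equal correlation of 0.9 among the changes themselves gives 8%, a patient-level shift of 2 SD gives 10%, and independent changes give 62%. Of the structures tried, only a noise-free straight line in each patient stays near 5% at n=3 (4.9%; 8.0% at n=6). The direction is certain; the size depends on the correlation.
- **A definition may sit in blacked-out text or in the table shells.** Possible. If the extreme cohort mean is meant, the error is smaller but remains.
- **The consequences are limited.** True. This is an open-label study with very small cohorts. By-visit summaries, shift tables and listings remain, and no DLT or escalation rule uses these p-values. That limits the severity but does not make the p-values correct.
- **Fixed visits have their own problems.** SAP VI.C carries the last value forward, including after death, and the DSMC may lengthen a rest period. Neither biases a fixed-visit test when nothing has changed, but both need a line in the SAP.

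**Conclusion.** The concern holds: as written, the rule does not deliver the 5% level at which it will be read. On the per-patient reading, false rejection at the planned minimum of three patients is about 11-25% with nine values, 9-17% with five and 8-11% with three. These figures assume normal data, all visits done, and correlation between a random walk and independence. Larger cohorts are worse: with nine values, 36-71% at n=6 and 70-95% at n=10. The Kruskal-Wallis comparison in X.A does not test against zero and is not affected in this way. This should be fixed before database lock; it affects the reported safety and pharmacodynamic conclusions, not the conduct of dose escalation.

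**What to change.** 1. Delete the paired t-test sentence in all three places (IX.B twice, X.A once).
2. Define maximum and minimum change as per-patient values over a stated visit window, and report them descriptively.
3. If p-values are wanted, test change from baseline, with a 95% CI, only at visits named in the SAP for each measure. For example: the last IMG-7289 dosing day and the seventh IMG-7289 rest day of Cycle 1 for blood measures and vital signs, and the first scheduled post-baseline marrow for marrow markers. Anchor the rest visit to that day so that an extended rest does not move it, and say whether carried-forward values enter the test.
4. Note that Sub-cohort 1w is still taking ATRA on Day 14, so that visit is not off treatment for it. Flag patients whose baseline count followed a transfusion or hydroxyurea, both of which Protocol 6.1.1 allows.
5. Leave the Kruskal-Wallis comparison as it is.

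The cost is SAP text and table shells; change by visit is already summarised, and SAP I.B allows changes until database lock. There will be fewer p-values, and effects at other visits, including cumulative effects in Cycles 2-4, will be described but not tested.

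The optional tests have limits:

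- Precision is low. The CI half-width is t(0.975, n−1)/√n SDs of the change: 4.303/√3 = 2.48 at n=3 and 2.776/√5 = 1.24 at n=5.
- Two fixed visits give about a 9-10% chance of at least one false positive (simulated 9.0-9.6%; 1 − 0.95² = 9.75% if independent).
- A fixed visit holds 5% only if baseline is not itself shifted. If transfusion raised every baseline by an assumed 1 SD, the test would reject 12-34% at n=3 (correlation 0 to 0.8) with no drug effect. Platelet tests, and white-cell tests after hydroxyurea, therefore need cautious reading.

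The descriptive core (steps 1 and 2) is enough by itself if the team does not need p-values.

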The intended dosing plan for high risk AML/MDS patients is predicated on the supposition that LSD1 must be maximally inhibited to achieve the greatest therapeutic benefit. The concentrations of LSD1 inhibitors such as IMG-7289 (free base) used to achieve maximal effects on growth, differentiation and apoptosis *in vitro* with primary patient-derived AML cells as well as AML cell lines are similar to concentrations that *in vivo* inhibit red cell, platelet and granulocyte production. It is therefore expected that high risk AML/MDS patients will require treatment at doses sufficient to induce profound thrombocytopenia and neutropenia. These drug-induced but reversible cytopenias can be managed clinically as needed with platelet and red cell transfusions as well as broad-spectrum antibiotics in the case of febrile neutropenia, as are already standard practices in the routine management of AML/MDS patients receiving intensive SOC chemotherapy.

The effects of IMG-7289 on normal myeloid haematopoiesis observed in non-clinical studies are expected in humans; these are pharmacodynamic effects of LSD1 inhibition by IMG-7289, thus are not regarded as adverse. These events, with the exceptions noted below, will not be considered DLTs.

Dose Limiting Toxicity (DLT): DLT is defined as any one of the following AEs that occurs during the first cycle of therapy and is considered by the Investigator to be possibly, probably or definitely related to IMG-7289.

- A clinically significant bleeding event;
- Any Grade 4 or 5 non-haematologic adverse event;

- Any Grade 3 non-haematologic adverse event with failure to recover to Grade 1 within 7 days of drug cessation, with the following exceptions:
 - ≥ Grade 3 nausea, vomiting or diarrhoea that responds to standard medical care
 - ≥ Grade 3 aesthenia lasting less than 14 days
- Any Grade 3 electrolyte abnormality unrelated to the underlying malignancy and persisting greater than 24 hours.

Patients who experience a dose limiting toxicity (DLT) will have their dose adjusted downward if the Medical Monitor and Principal Investigator deem it safe for the patient to continue on IMG-7289. To ensure a minimum of 3 Cycle 1 completers, and contingent on the number of prior DLTs within the sub-cohort/cohort, such patients may be replaced.

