11.2 Adverse Events

The Investigator is responsible for monitoring the safety of patients who have enrolled in the study and for accurately documenting and reporting information as described in this section. Patients will be instructed to report to the Investigator any AE that they experience. Investigators will ask about the occurrence of AEs at each visit. Investigators are required to document all AEs occurring during the clinical study, commencing with the first dose of IMG-7289 through to the End of Study Visit (scheduled at 28 days post last IMG-7289 dose). Adverse event recording will continue for patients

who discontinue study treatment early but remain in follow-up, until their End of Treatment, Pre-End of Study and End of Study Visits have been completed.

Note: Any medical event which occurs from the time of Informed Consent but prior to dosing with IMG-7289 must still be documented in the patient's medical notes and will be recorded on the appropriate medical history CRF pages.

Adverse events will be recorded on designated CRF pages. Each AE is to be characterised (i.e., verbatim term) and information provided regarding its seriousness, start and stop dates, intensity, outcome, and causal relationship with the study drug.

An AE is any undesirable physical, psychological or behavioral effect experienced by a patient during participation in an investigational study, in conjunction with the use of the drug or biologic, whether or not product-related. This includes any untoward signs or symptoms experienced by the patient from the time of first dose with IMG-7289 until completion of the study.

Adverse events may include, but are not limited to:

- Subjective or objective symptoms spontaneously offered by the patient and/or observed by the Investigator or medical staff
- Findings at physical examinations
- Laboratory abnormalities of clinical significance

Progression of underlying malignancy is not reported as an AE if it is consistent with the suspected progression of the underlying cancer. Clinical symptoms of progression may be reported as AEs if the symptom cannot be determined as exclusively due to the progression of the underlying malignancy or does not fit the expected pattern of progression for the disease under study. If there is any uncertainty about an AE being due to only the disease under study, it should be reported as an AE.

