Additionally, the Kaplan-Meier method will be used to analyze event-free survival (EFS) and overall survival (OS); Summaries will present the number (%) of subjects with events, the number (%) of subjects without events (censored), the median (95% CI) survival, and the probability of 6-month survival. OS is defined as the time interval between treatment start date and death date, and OS will be censored at the last date known alive. EFS is defined as the time interval between the date of treatment start and date of resistance, relapse, progression, or death. For subjects that do not have an event, EFS will be censored at the date of last tumor assessment prior to any concurrent cancer chemotherapy and transfusion.

IX. Safety Analysis

The safety and tolerability of IMG-7289 with and without ATRA will be assessed by the analysis of adverse events (AEs), as well as changes in physical examinations, vital signs, laboratory values and ECGs as detailed below, using the Safety Population.

A. Adverse Events

The AEs reported on the eCRFs will be coded using the latest version of MedDRA available to the sponsor at the time of study initiation (up-versioning will not occur), associating lower-level terms with preferred terms and system organ classes (SOC) by the primary hierarchy. The tables will display counts and percentages of subjects who reported at least one AE in each system organ class represented in the AE data. Within each system organ class, the tables will display the counts and percentages of subjects reporting at least one AE, as designated by the preferred terms.

In any given category (e.g., SOC or preferred term) a patient will be counted only once. If a patient has the same AE on multiple occasions, only the highest toxicity grade will be used. Similarly, only the most related event will be used. Percentages will be based on the number of patients in the subgroup of patients being tabulated and not the number of events. Summaries that are displayed by system organ class and preferred terms will be ordered by descending order of incidence of system organ class and preferred term within each system organ class.

Treatment-emergent adverse events will be summarized. Only those events with an onset date on or after the date on which IMG-7289 was first dispensed, and within 28 days of last IMG-7289 treatment are to be recorded on the AE eCRF; therefore, all reported AEs are expected to be treatment-emergent. However, if eCRF completion

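### SAP IX.B tabulates laboratory CTCAE grade shifts only by visit, so no visible planned table shows how many patients per cohort ever reach Grade 3-4 cytopenia

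*SAP*

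**What the plan says.** SAP IX.B (Other Safety Parameters) plans these laboratory displays:

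- Listings and summaries of values: "Laboratory values will be listed and summarized at each assessment".
- Shift tables by normal range and by CTCAE grade, the latter in these terms: "CTCAE toxicity grade, compared to baseline, will be summarized by visit".
- One shift that is not by visit, in investigator categories rather than grades: "Overall laboratory result shift from baseline (Normal, Abnormal clinically significant (CS), and Abnormal non-clinically significant (NSC)) will be summarized".
- A test on extremes: "P-value for test to assess maximum and minimum change from baseline within each cohort will be calculated using paired t-test".

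For adverse events, SAP IX.A uses a patient-level rule: "If a patient has the same AE on multiple occasions, only the highest toxicity grade will be used".

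Protocol 8.2.1 expects the intended doses to cause profound thrombocytopenia and neutropenia. It says of effects on normal myeloid haematopoiesis that they "thus are not regarded as adverse. These events, with the exceptions noted below, will not be considered DLTs". One of the listed DLTs is "A clinically significant bleeding event". Under Protocol 11.2, adverse events may include "Laboratory abnormalities of clinical significance".

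**The concern.** Safety is a primary objective, and deep cytopenia is the toxicity that the protocol itself predicts. The natural question for each cohort is how many patients reached Grade 3 or 4, and how many of those were already there at baseline. A by-visit shift table answers a different question: how many were at that grade on a given day. If nadirs are short and fall on different days in different patients, the same patients are spread over several columns, and no column shows the total.

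The AE tables do count each patient once at the highest grade, but only for events recorded as AEs. A cytopenia regarded as a pharmacodynamic effect, or as an abnormality present before treatment, may never be recorded as one. The laboratory tables may then be the main summary of this risk, and the patient-level count is missing from them.

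**Working it through.** **1. What each visible display gives.**

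| Display | Patient-level? | CTCAE grade? |
|---|---|---|
| Grade shift by visit (SAP IX.B) | No | Yes |
| Overall Normal / CS / non-CS shift (SAP IX.B) | Not by visit | No |
| Maximum and minimum change, paired t-test (SAP IX.B) | Yes, but it tests a mean change | No |
| Out-of-normal-range shift (Protocol 12.5) | Not stated | No |
| AE tables (SAP IX.A) | Yes | Yes, for recorded AEs only |
| Listings | Yes, by hand count | Derivable |

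No row is a planned table of worst post-baseline laboratory grade.

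**2. By-visit counts do not determine the ever-reached count.** Take a cohort of 3 (the minimum in SAP IV.C), all with the same baseline grade, and three visits. If each patient is at Grade 4 at a different visit, the table reads 1/3, 1/3, 1/3 and the ever-reached share is 3/3. If one patient is at Grade 4 at all three visits, the table is identical and the ever-reached share is 1/3.

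**3. Size under assumed rates.** The plan gives no figure to reproduce. Let p be the share at Grade 3-4 at a typical visit (assumed), K the number of post-baseline haematology visits, and rho the within-patient correlation between visits on a latent normal scale. The SoA for Cohort 1, Cycles 2-4 shows 6 haematology readings per cycle (pre-dose Day 1 and Days 4, 7, 9, 11, 14), so K = 6 stands for about one cycle and K = 24 for four.

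- Independent visits: ever = 1 - (1 - p)^K. For p = 0.10, K = 6: 1 - 0.9^6 = 0.469, and 0.469 / 0.10 = 4.7.
- Correlated visits: ever is the average over standard normal u of 1 - (1 - Phi((t - sqrt(rho) u) / sqrt(1 - rho)))^K, with t the normal quantile of p.
- Full persistence (rho = 1): ever = p, so the ratio is 1.0.

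Ratio of ever-reached share to single-visit share, K = 6:

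| p | rho = 0 | rho = 0.5 | rho = 0.8 | rho = 1 |
|---|---|---|---|---|
| 0.10 | 4.7 | 3.2 | 2.2 | 1.0 |
| 0.20 | 3.7 | 2.6 | 1.9 | 1.0 |
| 0.50 | 2.0 | 1.7 | 1.5 | 1.0 |
| 0.80 | 1.25 | 1.23 | 1.17 | 1.0 |

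For K = 24, p = 0.10 gives 9.2 (rho = 0) or 3.3 (rho = 0.8); p = 0.80 gives at most 1.25. The ratio cannot exceed 1/p, so threefold or more needs p of at most one third.

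**4. Dependence on timing.** Assume readings on Days 3, 5, 7, 9, 11 and 14, and one Grade 4 episode per patient lasting 3 days, with onset uniform over Days 3 to 14 (11 days). The onset windows that put a patient at Grade 4 on those days are 0, 2, 3, 3, 3 and 3 days long, 14 in total. The mean by-visit share is 14 / (6 x 11) = 14/66 = 21%, while every episode is seen at some visit (100%). In simulation, the highest single-visit share averages 60% in cohorts of 3 and 50% in cohorts of 6. For 6-day episodes the mean is 24/66 = 36% and the highest visit averages 81% in cohorts of 3.

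Now assume onset on Days 5 to 9 and a duration of at least 7 days. Every patient is at Grade 4 on Days 9 and 11, so the by-visit table itself shows 100%.

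**The case against.** A reader might infer that the plan understates Grade 3-4 cytopenia several-fold. The documents do not support that. They give no rate, and by-visit tables do not claim to estimate an ever-reached share, so the figure is omitted rather than misreported. The protocol's pharmacology also points partly towards persistence and shared timing: Protocol 3.7 reports a half-life of 4-5 days with continuing exposure through the rest week, and Protocol 8.2.1 calls abnormal counts inherent in AML and MDS and ties the kinetics to cell lifespan. It also says that counts recover rapidly, so full persistence is not established either.

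A reader might also infer that the tables would show a low percentage at every visit. The illustration contradicts this: the highest visit averages 60% to 81% for cohorts of 3 with 3- to 6-day episodes.

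Nor does it follow that cohorts cannot be compared on haematologic risk. SAP VI.K allows tests of haematologic markers among cohorts. SAP X.A compares maximum and minimum changes in PD parameters across dose-finding cohorts by Kruskal-Wallis, although its parameter list is redacted. Transfusions are summarised, febrile neutropenia admissions are assessed, clinically significant laboratory abnormalities can be AEs, and all values are listed. With about 40 patients a hand count is feasible.

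The visible SAP does not say that unscheduled values are excluded; it is silent on where they go. Redacted text directly before IX.B, and shells that were not available, could contain a worst-grade display.

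All of this stands against the size of the effect. It does not supply the missing summary. A change score is not a grade, admissions and transfusions are consequences rather than depth of cytopenia, and a count left to the reader is not a planned analysis of a primary safety endpoint.

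**Conclusion.** The point holds as a gap in the planned displays. In the visible text, laboratory CTCAE grade is tabulated only by visit, and the number of patients per cohort whose worst grade was 3 or 4 is not planned. The highest single-visit share bounds it from below, provided that missing visits do not change the denominators and carried-forward values (SAP VI.C) are set aside.

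The size of the gap is unknown. Under assumed rates it runs from none (1.0 times) to several-fold (about 9 times at p = 0.10, 24 independent visits), and about 1.2 to 2.0 times for p of 0.5 to 0.8 with rho from 0 to 0.8. Against the highest visit rather than a typical one it is smaller: 100/60 = 1.7 and 100/81 = 1.2 in the illustration for cohorts of 3.

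The case for change rests on fit to the question, not on a demonstrated distortion. The SAP already applies the highest-grade rule to AEs, and the expected cytopenias are the events most likely to fall outside the AE and DLT tables.

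**What to change.** In SAP IX.B, add a table by cohort of baseline CTCAE grade against worst post-baseline grade, with counts and denominators, at least for neutrophils, platelets and haemoglobin. Use all observed values, scheduled and unscheduled, and no carried-forward values. Present it for Cycle 1 and for the initially allowed cycles, and keep the by-visit shifts as supporting displays. If the shells already contain such a table, cite it in IX.B.

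The cost is SAP wording and one derived table from data already collected; the SAP may be modified until database lock. The downside is that the reported Grade 3-4 frequency may look less favourable. Crossing it with baseline grade shows how much was present before treatment.
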